## **Documentation of particular situations**

In order to reflect the body temperature results adequately in the verbatim term of the AEs, the following should be considered:

- A clinically significant increase in body temperature <38 °C should be documented as an AE with the verbatim "body temperature increased".
- A clinically significant increase in body temperature  $\ge$ 38 °C should be documented as an AE with the verbatim "fever" or "pyrexia".

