# 2.3.1.1 Important identified risks

# Cytokine release syndrome

Cytokine release syndrome (CRS) has been recognized as an identified risk for BNT411. It is classified as an important identified risk. CRS is associated with the intended MoA of BNT411 to modulate the immune system via a TLR7-signaling mediated release of a distinct type 1 IFN dominated spectrum of cytokines. The compound has been specifically developed not to activate a broad range of pyrogenic cytokines in the biologically active dose range.

In monkeys (studies SD\_18\_006 and SD\_18\_007), slight increase in body temperature was observed at doses (allometrically scaled to the human equivalent dose) corresponding to the two highest dose levels that will be applied in humans. In rats (studies SD\_18\_003 and SD\_18\_004), decreased motility and increased respiratory parameters were detected at doses (allometrically scaled to the human equivalent dose) which are 100-fold higher than the highest dose which will be administered in humans.

The sponsor expects elevation of serum levels of indicator cytokines in the majority of patients at biologically active dose levels of BNT411. Systemic effects caused by those cytokines are pharmacodynamic surrogates. Correlating with such laboratory changes, adverse events (AEs) such as mild-to-moderate, transient and manageable flu-like symptoms (e.g. arthralgia, body temperature increased, chills, dehydration, dizziness, fatigue, feeling cold, headache, hot flush, hyperhidrosis, influenza-like illness, myalgia, nausea, pyrexia, tachycardia, and vomiting) are expected to occur. For these clinical manifestations of cytokine elevation, the trial protocol implements management with analgesics or anti-pyretics at recommended commonly used doses.

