#### 6.6.1 Dose Limiting Toxicity for Part 1A

#### Non-immune-related AEs that are considered DLTs:

During the first treatment cycle, any toxicity that is of Grade 3 and that does not resolve to Grade 1 or lower within a week despite the use of medical intervention, or that is of Grade 4, but with exceptions as follows:

- The following events occurring during the DLT period ARE also considered a DLT:
  - o Arrhythmia: Grade >2 newly developed arrhythmia of any kind.
  - Absolute leucocyte count  $\geq 50 \times 10^9$ /L sustained for 14 days.
  - Hypotension of Grade 3 that persists for >4 hours and requires hospitalization.
- The following events occurring during the DLT period ARE **NOT** considered a DLT:
  - o Grade <3 nausea or vomiting controllable with anti-emetics within 72 hours.
  - Hypotension (systolic pressure <90 mm Hg) of Grade <3 that is of limited duration (less than 72 hours) or can be managed with hydration measures.
  - o Hypotension that requires a precautionary admission for observation after Grade 3 hypotension that persists for ≤4 hours.
  - o Grade 3 amylase and lipase elevations that are not accompanied by clinical signs/symptoms of pancreatitis.

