#### 9 Statistics

## 9.1 Statistical Hypotheses

No statistical hypotheses are planned to be tested in this trial.

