## **Documentation of particular situations**

Abnormal Laboratory Results and Vital Signs Values

Not every laboratory or vital signs abnormality needs to be documented as an AE. For laboratory/vital signs abnormalities, the following definitions and documentation rules apply:

A laboratory/vital signs abnormality is clinically significant if it:

- is a sign of a disease or syndrome. In this case, only the diagnosis of the causing disease or syndrome needs to be documented as an AE.
- results in specific symptom(s) but no diagnosis of a disease or syndrome can be made. In this case, only the symptom(s) need to be documented as AE(s).
- is not a sign of a disease or syndrome and does not result in specific symptoms but leads to a change in trial treatment or in a medical intervention. In this case, the laboratory/vital signs abnormality must be documented as an AE.

Any laboratory/vital signs abnormality for which none of the above-mentioned criteria are applicable are not clinically significant and should therefore not be documented as an AE.

Increased Body Temperature and Fever

The normal range for the body temperature is defined as >35°C to <38°C. For results within this range no source data entry for clinical significance is required, and no AE needs to be documented. If an investigator rates a body temperature result within this range as clinically significant, the clinical significance needs to be documented in the source data and an AE (e.g. with the term "body temperature increased") needs to be documented. For results out of this range, a source data entry for clinical significance is required and an AE needs to be documented. The AE should be described (verbatim) and rated (intensity) according to NCI CTCAE criteria v5.0:

- Fever Grade 1: 38°C 39°C
- Fever Grade 2:  $>39^{\circ}\text{C}$   $40^{\circ}\text{C}$
- Fever Grade 3:  $>40^{\circ}$ C for  $\leq 24h$
- Fever Grade 4: >40°C for >24h
- Fever Grade 5: death due to fever

Since fever is an anticipated reaction to BNT411 and the sponsor is very interested in details of body temperature changes, an increase of body temperature  $\geq 38$  °C should be rated as clinically significant and documented as an AE. Conversely, there should be very good reasons if an increase of body temperature  $\geq 38$  °C is rated as not clinically significant and is not documented as an AE.

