#### 12 Attachments

# 12.1 Management Recommendations in Case of a Cytokine Release Syndrome (CRS)

The following guidelines should serve as recommendations to trial physicians to monitor and manage a potential case of CRS. The guidelines should not replace any clinical decisions made by the physicians based on their sound clinical judgment depending on individual patient's situation. In any given situation, all measures must be taken by the trial physicians to ensure the optimal clinical management is delivered to the patients based on the diagnosis.

For assessment, reporting and analysis of CRS in connection with this trial, all events will be graded according to CTCAE version 5.0 as shown in Table 12-1.

Table 12-1: CRS grading per CTCAE version 5.0

Grading system	Grade 1	Grade 2	Grade 3	Grade 4	Grade 5
CTCAE version 5.0	Fever, with or without constitutional symptoms	Hypotension responding to fluids. Hypoxia responding to <40% FiO2	Hypotension managed with one pressor. Hypoxia requiring ≥40% FiO2	Life-threatening consequences; urgent intervention needed	Death

CRS Definition: A disorder characterized by fever, tachypnea, headache, tachycardia, hypotension, rash, and/or hypoxia caused by the release of cytokines.

For treatment recommendations for the management of CRS, the following guidelines are adapted based on the American Society for Transplantation and Cellular Therapy (ASTCT) Consensus Grading for Cytokine Release Syndrome and Neurologic Toxicity Associated with Immune Effector Cells. The CRS consensus grading of ASTCT (previously known as American Society for Bone Marrow Transplant) is given in Table 12-2 (Lee et al, 2019).

Table 12-2: American Society for Transplantation and Cellular Therapy CRS consensus grading

CRS parameter	Grade 1	Grade 2	Grade 3	Grade 4
Fever 	Temperature	Temperature	Temperature	Temperature
	≥38°C	≥38°C	≥38°C	≥38°C
		,	with	
Hypotension	None	Not requiring	Requiring vasopressor with	Requiring vasopressors
		vasopressors	or without vasopressin	(excluding vasopressin)
		ar	nd/or 	
Hypoxia	None	Requiring	Requiring high-flow nasal	Requiring positive
		low-flow nasal	cannula, facemask,	pressure (e.g., CPAP,
		cannula  or blow-	nonrebreather mask, or	BiPAP, intubation and
		by	Venturi mask	mechanical ventilation)

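### An isolated fever after BNT411 can be recorded either as pyrexia or as Grade 1 CRS, and the documents do not say how the two rules fit together, so the CRS rate by dose can depend on the term a site chooses.

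*Protocol*

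**What the plan says.** Three sets of rules meet on one event.

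- **Fever rule.** Protocol 10.3.3 (Documentation of particular situations) gives its reason: "Since fever is an anticipated reaction to BNT411 and the sponsor is very interested in details of body temperature changes". A rise to 38 °C or more should normally be rated clinically significant and entered as an AE; leaving it out needs very good reasons. The entry "should be documented as an AE with the verbatim 'fever' or 'pyrexia". Grades are 1 for 38–39 °C, 2 for above 39 up to 40 °C, 3 for above 40 °C lasting at most 24 h, and 4 for above 40 °C lasting longer.
- **Diagnosis-first rules.** Under AE and SAE Recording, the same section asks for a diagnosis in place of separate signs and symptoms. For a vital-sign abnormality that is a sign of a syndrome, "only the diagnosis of the causing disease or syndrome needs to be documented as an AE".
- **CRS grading.** Protocol 12.1 states: "For assessment, reporting and analysis of CRS in connection with this trial, all events will be graded according to CTCAE version 5.0". In Table 12-1, Grade 1 is "Fever, with or without constitutional symptoms", with no temperature or duration tier.

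On CRS, Protocol 2.3.1.1 says: "It is classified as an important identified risk". It is the only one listed. The DLT definitions in 6.6.1 and 6.6.2 cover a Grade 3 toxicity that has not fallen to Grade 1 within a week, "or that is of Grade 4, but with exceptions as follows". Fever is not among the exceptions. Section 6.6.5 pauses the trial for two Grade 4 AEs related to BNT411. SAP 8.5.2 summarises TEAEs by preferred term and worst grade. It defines no grouped term and no separate CRS summary.

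**The concern.** Fever is an expected effect of BNT411 and also the entry criterion for CRS. Protocol 2.3.1.1 lists pyrexia and chills among the expected consequences of cytokine elevation, under the CRS heading itself. Two careful sites could see the same fever, without hypotension or hypoxia, and enter different terms, each able to point to protocol text.

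What is at stake first is the by-dose summary of the main safety risk. If pyrexia and CRS sit on separate lines and the split between them varies by site, a difference in CRS rate between cohorts may reflect naming as well as dose. For very high fevers the recorded grade also differs. That reaches the Grade ≥3 TEAE count, which is part of the primary endpoint, and in a narrow case the DLT count and the pause count.

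**Working it through.** The documents give no CRS or fever rate, so there is no figure to reproduce. The check applies their own tables to one event under each term.

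**Step 1: does anything settle the term?** The diagnosis-first rules point to CRS, while the fever rule points to fever or pyrexia and does not mention CRS. No precedence is stated. Footnote 3 of Tables 1-7 and 1-8 and section 8.10 call for cytokine samples when CRS is suspected, but give no cut-off. Section 2.3.1.1 expects raised cytokines in most patients at active doses, so elevation alone does not separate the two. The ASTCT grading in Table 12-2 also starts at 38 °C. The choice is left to judgement.

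**Step 2: grade under each term.** Assumptions: the fever is isolated, with no hypotension, hypoxia or life-threatening features, and the investigator would accept cytokine release as the cause.

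| Isolated fever | Entered as fever/pyrexia | Entered as CRS | What differs |
|---|---|---|---|
| 38.5 °C | Grade 1 | Grade 1 | Term only |
| 39.5 °C | Grade 2 | Grade 1 | Term and grade |
| 40.3 °C for 12 h | Grade 3 | Grade 1 | Also the Grade ≥3 count |
| 40.3 °C for 30 h | Grade 4 | Grade 1 | Also the automatic DLT (in Cycle 1) and the pause count (if related to BNT411) |

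A Grade 3 fever lasts at most 24 h above 40 °C by definition. It becomes an automatic DLT only if it then fails to reach Grade 1 within a week.

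**Step 3: escalation.** Under Table 4-1, one event of the last kind moves a cohort from 0/3 (escalate) to 1/3 (expand), or from 1/6 (escalate) to 2/6 (stop).

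To show scale, let q be the per-patient Cycle 1 probability of such a fever. This is an assumption, because the documents give no value. With total DLT probability p,

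P(escalate) = (1−p)³ + 3p(1−p)² × (1−p)³.

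With no other DLTs, p = q if the event is named fever and p = 0 if it is named CRS. With an assumed 10% rate of other DLTs, p = 1 − 0.9(1−q) if named fever and p = 0.10 if named CRS.

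| q | Fever, no other DLTs | CRS, no other DLTs | Fever, 10% other DLTs | CRS, 10% other DLTs |
|---|---|---|---|---|
| 2% | 0.995 | 1.000 | 0.875 | 0.906 |
| 5% | 0.973 | 1.000 | 0.824 | 0.906 |
| 10% | 0.906 | 1.000 | 0.730 | 0.906 |
| 20% | 0.709 | 1.000 | 0.536 | 0.906 |

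For q = 5% with no other DLTs: 0.857 + 3 × 0.05 × 0.9025 × 0.857 = 0.973. The effect is small if such fevers are rare. The figures compare uniform naming one way with uniform naming the other, and assume that no discretionary DLT call is made.

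**Step 4: does the SAP pool the terms?** No. SAP 8.5.2 counts by preferred term and worst grade. SAP 8.5.4 summarises body temperature by cohort and time point, but not as AE incidence or grade.

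**The case against.** The case on the other side has real force.

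- **The rules can be read together.** The fever rule's stated purpose is to make the verbatim term reflect the temperature, separating body temperature increased (below 38 °C) from fever or pyrexia. Diagnosis-first could then govern any event judged to be CRS.
- **Table 12-1 grades; it does not define cases.** The definition printed with it requires cytokine release as the cause. A reader might infer that all BNT411 fevers must be called pyrexia and are all CRS as well, a flat contradiction. The documents do not support that. The fever rule allows exceptions, and a CRS entry needs a causal judgement.
- **Safeguards exist.** Section 6.6 allows other clinically significant toxicities to be treated as DLTs. Sections 6.6.1 and 6.6.2 let the investigator and sponsor judge any other toxicity a DLT. Under 4.1.1.1 the Safety Review Committee sees all relevant safety and clinical data. Section 10.3.3 excepts severe or serious secondary events from recording by primary cause alone, so a severe fever might be entered beside CRS.
- **The analysis is descriptive.** Protocol 9.1: "No statistical hypotheses are planned to be tested in this trial". Body temperature is summarised and all AEs are listed.

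Most of this stands, and it narrows the point. What remains is that nothing states how diagnosis-first applies to the fever rule, and no criterion separates cytokine-related fever from CRS. The safeguards name neither fever nor CRS. They can rescue an individual decision but do not make recording consistent.

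**Conclusion.** The point holds as a gap in how the recording rules fit together. When an investigator attributes an isolated fever to cytokine release, the documents support two terms and, above 39 °C, two grades, without saying which applies.

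The CRS rate by dose is exposed at any temperature from 38 °C. The Grade ≥3 count is exposed only above 40 °C. The automatic DLT and the Grade 4 pause count are exposed only above 40 °C for more than 24 h, the DLT only within Cycle 1. That last case is probably uncommon and is partly covered by discretion.

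Two stronger inferences should be resisted. One is that DLT decisions in general turn on naming; the tables show this only for the narrow case above. The other is that a specific distortion of the CRS rate can be quoted; the documents give no fever or CRS frequencies, and the escalation figures rest on assumed values. The conclusion assumes no hypotension, hypoxia or life-threatening features, since those would raise the CRS grade. This is a worthwhile, inexpensive improvement and does not undermine the design.

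**What to change.** 1. **SAP 8.5.2.** Add one table by cohort and worst grade for a prespecified grouped term covering at least CRS, pyrexia and body temperature increased. Show it beside the individual terms and use the AE grades as recorded. Cost: one extra output, and a pooled term less specific than CRS because it also takes in fevers with other causes. The table makes the count of affected patients largely independent of the term chosen. It does not make the grade independent: where only CRS was entered, a temperature-based AE grade cannot be assumed to exist.
2. **Protocol 10.3.3 and 12.1.** Reconcile the fever rule with the diagnosis-first rules and Table 12-1. State which term is recorded and which grade feeds the DLT and pause assessments. The choice of clinical rule is for the sponsor, and none is proposed here. Cost: a short protocol clarification and an eCRF completion note. It would guide later recording and would not recode events already entered.

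SAP section 3 says Part 2 is no longer applicable, so the first step is the more useful: it works on the Part 1 AE data as coded.

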#### Deaths

All deaths that occur during the period of observation must be recorded on the AE eCRF and immediately reported as an SAE to the sponsor, regardless of relationship to trial treatment. In addition to reporting as an SAE, the applicable eCRF must be completed.

Exemptions to the SAE definition, as defined in Section 10.3.3, also apply for fatal cases

Death should be considered an outcome ("fatal") and not a distinct event. The event or condition that caused or contributed to the fatal outcome should be recorded as the single medical event on the AE eCRF. If there is more than one AE in a fatal case, the outcome "fatal" should be selected only for the AE leading to death.

If the cause of death is unknown and cannot be ascertained at the time of reporting, "unexplained death" should be recorded on the AE eCRF. If the cause of death becomes available later (e.g., after autopsy), "unexplained death" should be replaced by the established cause of death. The term "sudden death" should not be used unless combined with the presumed cause of death (e.g., "sudden cardiac death").

Deaths that occur after the AE reporting period should be recorded on the applicable eCRF, regardless of cause.

*In Germany only:* Any death, irrespective if causally related to disease progression or not, will be documented as AE and reported as SAE.

• Adverse Events Associated with an Overdose or Error in Drug Administration

An overdose is the accidental or intentional use of a drug in an amount (per administration or cumulatively) higher than the dose being studied (for BNT411) or higher than the maximum recommended dose according to the authorized product information (for approved concomitant medications). An overdose or incorrect administration of a drug is not itself an AE, but it may result in an AE. Intentional overdoses taken with possible suicidal/self-harming intent should be reported regardless of sequelae. All AEs associated with an overdose or incorrect administration should be documented as an AE in the source data and eCRF and reported as SAE if applicable.

## Follow-up of AEs and SAEs

- The investigator is obligated to perform or arrange for the conduct of supplemental measurements and/or evaluations as medically indicated or as requested by the sponsor to elucidate the nature and/or causality of the AE or SAE as fully as possible. This may include additional laboratory tests or investigations, histopathological examinations, or consultation with other health care professionals.
- If a patient dies during participation in the trial or during a recognized follow-up period, the investigator will provide the sponsor with a copy of any post-mortem findings (including histopathology) if an autopsy or any other testing has been performed.
- New or updated information will be recorded in the originally completed eCRF.
- The investigator will submit any updated SAE data to the contacts given in Section 10.3.4 within 24 hours of receipt of the information.

## **SAE Reporting to Sponsor**

- Information for final description and evaluation of a case report may not be available within the required time frames for reporting. Nevertheless, for regulatory purposes, initial reports should be submitted if the following minimal information is available:
  - An identifiable subject (number, initials)
  - A suspected medicinal product
  - An identifiable reporting source (investigator/trial site identification)
  - An event or outcome that can be identified as serious
- After the initial AE/SAE report, the investigator is required to proactively follow each subject at subsequent visits/contacts. If additional information regarding a previously submitted SAE is obtained, a follow-up SAE report should be sent to the sponsor (indicating that this is a "follow-up" report) without delay and accompanied by appropriate anonymous supporting documentation (e.g., hospital reports), until a final outcome and date are available.
- Completed reporting forms need to be signed by an investigator before faxing/mailing them to the safety contact provided above. Blank reporting forms are provided to the investigator during the site initiation visit and are filed in the Investigator Site File (ISF).
- If any medical records (for example hospital discharge reports) are considered as relevant case information by the investigator, it is recommended that the investigator directly provides the medical report to the contact details described above. In the case of an SAE including a hospital stay for the subject, the respective discharge letter needs to be provided by the site as soon as it is available, at a minimum. To ensure clear allocation of the record to a specific subject and SAE, the investigator should additionally complete and sign a paper follow-up form (titled: Additional Information and Follow-Up Form) and provide the follow up form together with the pseudonymized medical record.
- Original, completed reporting forms have to be filed in the ISF, with copies in the Trial Master File. All events initially reported on a paper-based reporting form also have to be documented in the eCRF.
- If explicitly required according to national legislation, the investigator must submit copies of the SAEs to the ethics committee (EC) or authority and retain documentation of these submissions in the Site Trial File.

## 10.4 Appendix 4: Definition of Reproductive Potential and Contraception

Definition of reproductive potential and measures of contraception for BNT411 are detailed below. Further guidance for other trial treatment agents should be according to the authorized product information (for approved concomitant medications).

## **Female Patients**

In this trial, patients are considered to have reproductive potential, UNLESS they are post-menopausal or permanently sterile:

- A postmenopausal state is defined as no menses, in patients >45 years of age, for 12 months without an alternative medical cause. A high follicle stimulating hormone (FSH) level in the postmenopausal range may be used to confirm a post-menopausal state in patients not using hormonal contraception or hormonal replacement therapy. However, in the absence of 12 months of amenorrhea, a single FSH measurement is insufficient.
- Permanent sterilization methods include hysterectomy, bilateral salpingectomy and bilateral oophorectomy.

All female patients must agree not to donate eggs (ova, oocytes) for the purpose of assisted reproduction during the trial and for 6 months after receiving the last dose of BNT411.

Female patients of reproductive potential must agree to use adequate contraception during and for 6 months after the last BNT411 administration. Adequate contraception is defined as highly effective methods of contraception (Table 10-2). Birth control methods are considered highly effective if they have a failure rate of less than 1% per year, when used consistently and correctly.

